#### 6.1.1.2 Listings

Unless specified otherwise, by-subject listings are sorted by randomization status (randomized, not randomized), site-subject ID, and additional variables such as time points, as applicable. Listings display as-randomized treatment group abbreviated as (1) "ZAV100" for zavegepant 100 mg, "ZAV200" for zavegepant 200 mg, "PBO100" for placebo 100 mg, and "PBO200" for placebo 200 mg for subjects in the full analysis set, and (2) "NRND" for subjects not in the full analysis set.

Listings of significant protocol deviations, exposure, safety parameters, and outcomes research parameters include the following: abbreviated name of the analysis period in which the measurement was slotted (i.e., PRETRT, DBT, INT, OLZAV, FU; this does not apply to exposure); analysis visit in which the measurement was slotted (this does not apply to exposure

or AEs); measurement date/time; study day derived from the measurement date, and zavegepant study day  $\geq 1$  derived from the measurement date for as-randomized placebo subjects.

#### 6.1.2 Statistical Methods

Refer to the Core SAP for descriptive statistics in summary tables, counting rules in frequency tables, and rounding rules in frequency tables.

## 6.1.3 Missing Data

All analyses are based on observed data unless otherwise specified. See Section 6.3 for statistical methods for handling missing data in efficacy analyses.

## 6.2 Study Population

Refer to the Core SAP for TLF contents.

## 6.2.1 Analysis Sets

The frequency table of analysis sets described in Section 4.1 is provided by treatment group plus placebo pooled (as-randomized for the randomized, full, efficacy, and migraine analysis sets; astreated for all safety analysis sets), not randomized, and overall.

See Section 6.3.1 for months.

The by-subject listing of analysis sets is provided for the enrolled analysis set.

The administrative listing of randomization scheme and codes is provided for the full analysis set.

#### 6.2.2 Enrollment

Frequency table of enrollment by country and site is provided for the enrolled analysis set, and also displays results for the full and safety analysis sets.

## 6.2.3 Subject Disposition

The by-subject listing of subject discontinuation is provided for the enrolled analysis set and displays a separate record for each study phase (i.e., DBT, OLE and Follow-up) that is discontinued (i.e., completed or not completed) corresponding to each type of subject status CRF. The listing includes the following:

- Relevant reference dates: i.e., last contact date\*, IWRS randomization date
- Study phase: DBT, OLE, or Follow-up. For each study phase:
  - Last visit date. Derived from visit dates from the Visit Date and Unscheduled Visit Checklist CRFs as follows:
    - DBT Phase: latest visit date in the pretreatment or on-DBT safety analysis period

- OLE Phase: latest visit date in the OL zavegepant safety analysis period
- Follow-up Phase: latest visit date in the follow-up safety analysis period
- O Phase completion status: "completed"; or "not completed" concatenated with the reason for non-completion (see Sections 6.2.3.1, 6.2.3.2, 6.2.3.3, 6.2.3.4, and 6.2.3.5)
- Next phase continuation status: "continued" concatenated with the name of the next phase (OLE or Follow-up); or "not continued" concatenated with the reason for non-continuation (see Sections 6.2.3.2, 6.2.3.3, and 6.2.3.4). This does not apply to the Follow-up Phase.

A footnote describes the derivation of the last contact date as "\* Derived as the death date (if it exists); otherwise, the maximum date collected across study population, efficacy safety, and outcomes research parameters". See Section 7.1 for derived dates and Section 7.2 for analysis periods.

## 6.2.3.1 Subject Disposition from Enrollment to Randomization

The frequency table of subject disposition from enrollment to randomization is provided for the enrolled analysis set based on the DB Subject Status CRF, and displays the following categories:

- Randomized (identified as subjects with nonmissing IWRS randomization date)
- Not randomized (identified as subjects with missing IWRS randomization date)
  - Reasons for discontinuation (i.e., not completing the DBT Phase), including not reported. For subjects whose reason is screen failure due to inclusion/exclusion criteria, the reasons for screen failure from the Inclusion/Exclusion CRF are also displayed as subcategories.

## 6.2.3.2 Subject Disposition from Randomization to Treatment

The frequency table of subject disposition from randomization to treatment is provided by treatment group and overall for the full analysis set based on the DB Subject Status CRF, and displays the following categories:

- Treated with study drug (identified as subjects with nonmissing study drug start date)
- Not treated with study drug (identified as subjects with missing study drug start date)
  - o Reasons for discontinuation (i.e., not completing the DBT Phase), including not reported

#### 6.2.3.3 Subject Disposition during the DBT Phase

The frequency table of subject disposition during the DBT Phase is provided for the DBT safety analysis set by as-treated treatment group, zavegepant pooled, placebo pooled, and overall based on the DB Subject Status CRF, and displays the following categories:

- Ongoing in the DBT Phase. These are identified as subjects with (1) missing response to the question "Did the subject complete the DBT Phase?" and (2) missing DB study drug last date. This category only exists before the LSLV database lock. After the LSLV database lock, subjects with missing response are categorized as "Did not complete the DBT Phase".
- Completed the DBT Phase. These are identified as subjects with (1) "yes" response to the question "Did the subject complete the DBT Phase?" and (2) nonmissing DB study drug last date.
- Did not complete the DBT Phase. These are identified as subjects with (1) "no" or missing response to the question "Did the subject complete the DBT Phase?" and (2) nonmissing DB study drug last date.
  - o Reasons for not completing the DBT Phase, including not reported
- Continued to the next phase. These are identified as subjects with (1) "yes" response to the question "Is the subject continuing to the Follow-up Phase?" and missing response to the question "Is the subject continuing to the next phase?", or (2) "yes" response to the question "Is the subject continuing to the next phase?".
  - Next phase, i.e., OLE or Follow-up. The next phase is determined from the response to the "If Yes, select the next phase" question, if available. Otherwise, if there is a "yes" response to the question "Is the subject continuing to the Follow-up Phase?", then the next phase is considered to be Follow-up.
- Did not continue to the next phase. These are identified as subjects with (1) missing response to the question "Is the subject continuing to the next phase?" and "no" response to the question "Is the subject continuing to the Follow-up Phase?", or (2) "no" response to the question "Is the subject continuing to the next phase?", or (3) after the LSLV database lock, missing responses to both questions about continuing.
  - Reasons for not continuing to the next phase, including not reported. These are based on reasons for not continuing to the Follow-up Phase or the next phase.

## 6.2.3.4 Subject Disposition during the OLE Phase

The frequency table of subject disposition during the OLE Phase is provided by OL zavegepant dose and overall for the OL zavegepant safety analysis set based on the OLE Subject Status CRF, and displays the following categories:

- Ongoing in the OLE Phase. These are identified as subjects with (1) missing response to the question "Did the subject complete the OLE Phase?" and (2) missing OL zavegepant last date. This category only exists before the final database lock; otherwise, subjects with missing response are categorized as "Did not complete the OLE Phase".
- Completed the OLE Phase. These are identified as subjects with (1) "yes" response to the question "Did the subject complete the OLE Phase?" and (2) nonmissing OL zavegepant last date.

- Did not complete the OLE Phase. These are identified as subjects with (1) "no" or missing response to the question "Did the subject complete the OLE Phase?" and (2) nonmissing OL zavegepant last date.
  - o Reasons for not completing the OLE Phase, including not reported
- Continued to the Follow-up Phase. These are identified as subjects with "yes" response to the question "Is the subject continuing to the Follow-up Phase?".
- Did not continue to the Follow-up Phase. These are identified as subjects with (1) "no" response to the question "Is the subject continuing to the Follow-up Phase?", or (2) after the LSLV database lock, missing response to the question "Is the subject continuing to the Follow-up Phase?".
  - o Reasons for not continuing to the Follow-up Phase, including not reported.

## 6.2.3.5 Subject Disposition during the Follow-up Phase

The frequency table of subject disposition during the Follow-up Phase is provided by as-treated treatment group/OL zavegepant status and overall for the follow-up safety analysis set based on the Follow-up Subject Status CRF, and displays the following categories:

- Did not formally enter the Follow-up Phase. These are identified as subjects with missing response to the question "Did the subject complete the Follow-up Phase?", and any of the following:
  - "No" response to the question "Is the subject continuing to the Follow-up Phase?" and missing response to the question "Is the subject continuing to the next phase?" on the DB Subject Status CRF
  - "No" response to the question "Is the subject continuing to the next phase?" on the DB Subject Status CRF
  - o "No" response to the question "Is the subject continuing to the Follow-up Phase?" on the OLE Subject Status CRF.

A footnote explains that these are subjects with data in the follow-up safety analysis period who did not continue to the Follow-up Phase as per DB or OLE Subject Status CRF.

- Ongoing in the Follow-up Phase. These are identified as subjects with missing response to the question "Did the subject complete the Follow-up Phase?", and who are not already categorized as "Did not formally enter the Follow-up Phase".
  - This category only exists before the final database lock. After the final database lock, these subjects are categorized as "Did not complete the Follow-up Phase".
- Completed the Follow-up Phase. These are identified as subjects with "yes" response to the question "Did the subject complete the Follow-up Phase?".
- Did not complete the Follow-up Phase. These are identified as subjects with "no" response to the question "Did the subject complete the Follow-up Phase?".

o Reasons for not completing the Follow-up Phase, including not reported

0

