4.3.4 Follow-up Phase

The Follow-up Phase will have 2 scheduled visits, Follow-up Week 2 and Follow-up Week 8. These visits should occur approximately 2 weeks and 8 weeks, respectively, after the last visit

in the last treatment phase (i.e., Week 12/EOT Visit [+3 days] if the subject did not enter the OLE Phase; Week 64/EOT Visit [+/- 2 days] if the subject entered the OLE Phase).

All randomized subjects should complete both follow-up visits, regardless of completing either treatment phase.

Subjects will continue to record all concomitant medications, including standard of care migraine medications (both prophylactic and acute, prescribed and OTC), taken during the entire Follow-up Phase in a concomitant medication paper diary.

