#### **Intercurrent Events**

Intercurrent events are those that occur after treatment initiation and either preclude observation of the endpoint or affect its interpretation.

Study drug discontinuation before the time point of interest defining the endpoint is considered an intercurrent event.

• For efficacy objectives assessed with a continuous endpoint during the DBT Phase, study drug discontinuation is handled with a "hypothetical strategy," i.e., the hypothetical scenario is that had subjects not discontinued DB study drug, their efficacy would have been similar to the efficacy of subjects from the same treatment group and randomization stratum who did not discontinue DB study drug. All observed values of the endpoint of interest are excluded after DB study drug discontinuation (see Section 7.2), and statistical methods are used to estimate the treatment effect that would have been seen had the intercurrent event not occurred.

- For efficacy objectives assessed with a binary endpoint during the DBT Phase, DB study drug discontinuation is handled with a "composite strategy," i.e., the occurrence of the intercurrent event is integrated as a component of the endpoint. All observed values of the endpoint of interest are excluded after DB study drug discontinuation (see Section 7.2), and subjects with missing data are considered failures.
- For safety objectives, study drug discontinuation is handled with a "while-on-treatment strategy". All observed values of the endpoint of interest are used on or before study drug discontinuation + 7 days (see Section 7.2 and the Core SAP).
- For outcomes research and other objectives, study drug discontinuation is handled with a "treatment policy strategy", i.e., the occurrence of the intercurrent event is considered irrelevant, such that all observed values of the endpoint of interest are used regardless of study drug discontinuation.

Non-study prophylactic migraine medication use before the time point of interest defining the endpoint is also considered an intercurrent event. For all objectives, this intercurrent event is handled with a treatment policy strategy, such that all observed values of the endpoint of interest are used.

Nonstudy acute migraine-specific medication use before the time point of interest defining the endpoint is also considered an intercurrent event, except for efficacy objectives based on acute migraine-specific medication days or acute migraine medication days.

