# 4 ANALYSIS SETS, TREATMENT GROUPS, AND SUBGROUPS

# 4.1 Analysis Sets

The following analysis sets are evaluated and used for presentation and analysis of the data:

- Enrolled: Subjects who sign an informed consent form and are assigned a subject identification number, i.e., nonmissing informed consent date. This analysis set is used mainly to assess study population and in by-subject listings.
- Full: Subjects in the enrolled analysis set who receive a randomized treatment assignment from the IWRS, i.e., nonmissing IWRS randomization date. This analysis set is used mainly to assess study population.
- Safety: Subjects in the enrolled analysis set who take ≥ 1 dose of study drug (zavegepant or placebo), i.e., nonmissing study drug start date. This analysis set is used to assess study population and produce select by-subject listings.
  - O DBT safety: Subjects in the safety analysis set who take ≥ 1 dose of DB study drug (zavegepant or placebo), i.e., nonmissing DB study drug start date. This analysis set is used to assess study population, exposure, and on-DBT safety.
  - OL zavegepant safety: Subjects in the safety analysis set who take ≥ 1 dose of OL zavegepant, i.e., nonmissing OL zavegepant start date. This analysis set is used to assess study population, exposure, and on-OL zavegepant safety.
    - Interim safety: Subjects in the OL zavegepant safety analysis set with OL zavegepant start date DB study drug last date > 7 days. This analysis set is used to assess post-DBT pre-OL zavegepant safety.
  - DB or OL zavegepant safety: Subjects in the safety analysis set who take ≥ 1 dose of DB or OL zavegepant, i.e., nonmissing DB or OL zavegepant start date. This analysis set is used to assess exposure and on-DB or OL zavegepant safety.
  - o Follow-up safety: Subjects in the safety analysis set whose last contact date is in the follow-up safety analysis period. This analysis set is used to assess follow-up safety.
- DBT efficacy: Subjects in the full analysis set who are randomized only once and take ≥ 1 dose of DB study drug (zavegepant or placebo). This analysis set is used mainly to assess DBT outcomes research.

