  - 2. Otherwise, the latest complete date of the following: AE start or end; ECG; eDiary finding; informed consent; IWRS randomization; laboratory test collection; non-study medication start or end; physical exam; physical measurement; procedure; rating scale; questionnaire; study medication start or end; vital sign; visit.
  - 3. If the last contact date is after the most recent raw database creation date, then it is set to the most recent raw database creation date.
- Death date: refer to the Core SAP.

No imputations are performed on these derived dates, unless specified otherwise.

Refer to the Core SAP for the definition of complete dates.

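### The Follow-up disposition table omits subjects who continued to Follow-up but have no dated record in that period, and no planned frequency table counts them or their reasons for loss

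*SAP*

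**What the plan says.** SAP 6.2.3.5 provides the Follow-up disposition table "for the follow-up safety analysis set based on the Follow-up Subject Status CRF". SAP 4.1 defines that set as "Subjects in the safety analysis set whose last contact date is in the follow-up safety analysis period".

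In SAP 7.1 the last contact date is the death date if one exists. The rule then reads "Otherwise, the latest complete date of the following: AE start or end; ECG; eDiary finding; informed consent; IWRS randomization", and the list goes on to laboratory, medication, procedure, questionnaire, visit and similar dates. It names no date from a Subject Status form.

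SAP 7.2 leaves the definition of the follow-up safety period to the Core SAP, which was not supplied. The on-treatment rule in SAP 3.2 reads "All observed values of the endpoint of interest are used on or before study drug discontinuation + 7 days", and the first follow-up window in SAP Table 5 opens at follow-up day 8. The period therefore appears to start more than 7 days after the last dose.

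Inside the table there is a row for subjects who did not formally enter Follow-up: "A footnote explains that these are subjects with data in the follow-up safety analysis period who did not continue to the Follow-up Phase". Subjects with no completion response are first shown as ongoing. "This category only exists before the final database lock"; after that they count as non-completers.

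Protocol 4.3.4 sets the expectation: "All randomized subjects should complete both follow-up visits, regardless of completing either treatment phase". SAP 6.2.3.3 covers the whole DBT safety set and reports continuation by destination ("Next phase, i.e., OLE or Follow-up"). SAP 6.2.3.4 reports continuation to Follow-up for the whole open-label safety set.

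**The concern.** The table reports how many subjects completed Follow-up, but it admits only subjects who were seen, or left some dated trace, during Follow-up. The earliest losses are therefore the ones it cannot show. A negative answer on the Follow-up Subject Status form, with a reason such as lost to follow-up, does not reach the table if nothing else is dated in the period. The rule that turns a missing response into non-completion does not help, because it works only within the set.

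The section provides for one mismatch (data in the period without formal entry) but not for its mirror image (formal entry without data).

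At stake is how a reader judges the completeness of post-treatment safety surveillance. The follow-up tables of AEs, laboratory abnormalities, LFT elevations and C-SSRS (SAP 6.4.1.5, 6.4.2.1, 6.4.2.2 and 6.4.5) use the same set. Protocol 4.3.4.1 and 4.3.4.2 schedule LFTs at both follow-up visits.

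**Working it through.** The plan states no follow-up completion rate, so there is no figure to reproduce. The check is on the denominator.

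**Notation**
- C: subjects who completed Follow-up
- I: formal entrants with a contact in the period who did not complete
- L: formal entrants with no contact in the period (outside the set)
- U: subjects in the set who did not formally enter (never completers, since the row requires a missing completion response)
- W: other treated subjects outside the set

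**Assumptions.** Percentages use the set size as denominator (counting rules are in the Core SAP). A completer has a dated follow-up visit and so is always in the set.

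**Three rates**
- Table: C / (C + I + U)
- Formal entrants: C / (C + I + L)
- All treated: C / (C + I + U + L + W)

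**Direction.** The numerator is the same throughout, so only the denominators matter.
- Table against all treated: the table's denominator is smaller by L + W, so its rate is never below the all-treated rate.
- Table against formal entrants: the table is higher if L > U, equal if L = U, and lower if L < U.

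**Illustration.** The inputs are assumed, with C + I = 1000 and W = 0:

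| C | L | U | Table | Formal entrants | All treated |
|---|---|---|---|---|---|
| 950 | 50 | 0 | 950/1000 = 95.0% | 950/1050 = 90.5% | 950/1050 = 90.5% |
| 950 | 100 | 0 | 950/1000 = 95.0% | 950/1100 = 86.4% | 950/1100 = 86.4% |
| 950 | 50 | 20 | 950/1020 = 93.1% | 950/1050 = 90.5% | 950/1070 = 88.8% |
| 950 | 50 | 50 | 950/1050 = 90.5% | 950/1050 = 90.5% | 950/1100 = 86.4% |
| 950 | 20 | 50 | 950/1050 = 90.5% | 950/1020 = 93.1% | 950/1070 = 88.8% |
| 850 | 50 | 0 | 850/1000 = 85.0% | 850/1050 = 81.0% | 850/1050 = 81.0% |
| 850 | 20 | 50 | 850/1050 = 81.0% | 850/1020 = 83.3% | 850/1070 = 79.4% |

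**Can other output supply L?** Only in part.
- SAP 6.2.1 tabulates the size of every analysis set. Safety minus follow-up safety gives L + W, without separating the two.
- SAP 6.2.3 lists Follow-up completion status and reason by subject where a status form exists, but gives no counts.
- Subtracting SAP 6.2.3.5 from the continuation counts in 6.2.3.3 and 6.2.3.4 is not exact. The OLE table is by open-label dose, which merges former zavegepant and former placebo subjects, while SAP Table 4 splits the follow-up set by treatment group and open-label status. After lock, missing continuation answers count as not continuing in 6.2.3.3 and 6.2.3.4. In 6.2.3.5 the row for not formally entering needs an explicit negative answer, so a subject missing both the continuation and the completion answers falls under non-completion instead.

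**The case against.** The strongest reply is that most of this can be found elsewhere and that nothing important rests on it. Much of that stands.

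- A reader might infer that nobody can tell how many treated subjects are missing from the follow-up safety tables. The documents do not support that. The analysis-set table in SAP 6.2.1 shows it by group, and a by-subject listing of set membership accompanies it.
- A reader might infer that these subjects have no category anywhere. That is true of this table only. They are counted as continuing in SAP 6.2.3.3 or 6.2.3.4, and their reasons can appear in the SAP 6.2.3 listing.
- A reader might infer that the completion rate is simply overstated. Among formal entrants this is not established, because subjects who did not formally enter pull the percentage down. With L = 20 and U = 50 in the illustration, the table reads lower than the entrant rate.
- It is tempting to size the problem from the planned 1440 randomized and 1200 entering the OLE: 240/1440 = 16.7%. That group is not this table's population. OLE subjects also go on to Follow-up. Protocol 4.3.3 notes that some subjects had already entered Follow-up before the OLE was added. SAP 1 records early termination in December 2023.
- Some entrants who are never seen again remain in the set, for example when the EOT visit or a medication end date falls inside the period.
- Secondary safety objectives 7 to 9 are assessed on treatment (SAP 3.2.2), and follow-up completion is not an endpoint.

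What the reply does not remove is that no planned frequency table counts the early follow-up losses or their reasons, and that this is the one phase-disposition table conditioned on later contact.

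**Conclusion.** The point holds as a limited, descriptive weakness. The Follow-up disposition table excludes formal entrants with no dated record in the follow-up safety period, and their reasons with them. Against all treated subjects, its completion percentage is at or above the true rate. Among formal entrants the direction depends on whether L exceeds U.

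The size is unknown. L, U and the Core SAP rules are not in the documents, and the percentages above only illustrate the mechanism. The conclusion assumes that the set size is the denominator and that completers always have a dated follow-up contact. The 7-day boundary is inferred, but the exclusion does not depend on the exact day. Efficacy estimates and the on-treatment safety objectives are unaffected.

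**What to change.** In SAP 6.2.3.5, base the table on the safety analysis set. An alternative base is all subjects recorded as continuing to Follow-up, plus those with follow-up data who did not formally enter. Keep the present rows, add one for subjects who continued to Follow-up but had no contact in the follow-up safety period, and show reasons for every negative completion response.

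If the safety set is used, widen the existing row for not formally entering so that it also takes non-entrants without follow-up data, rather than adding an overlapping row. State which row receives subjects with a missing continuation answer, so that the table agrees with SAP 6.2.3.3 and 6.2.3.4.

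The cost is a new denominator and one extra row in one table, built from CRF fields that SAP 6.2.3 already uses. The downside is a slightly less favourable reported follow-up completion.
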